**Selection of Phase 2b Study Population:**

**Inclusion Criteria:**

1. Male or female aged 18 to 80 years, inclusive, at the time of consent.
2. Have a physician-documented diagnosis of PN that is confirmed by review of medical photography (as outlined in the Study Manual) during the Screening Period. Duration of PN (since the time of first PN nodule) must be at least 6 months from the time of first PN nodule to Day 1, as affirmed by the subject.
3. Have at least 20 nodules of approximately 0.5 to 2 cm at the Screening Visit and Day 1. The nodules must be pruritic and present on at least 2 different anatomical locations (not be localized), involve the extremities, with extensor extremity involvement greater than the flexor extremity involvement. Nodules on the head (face and scalp) are not counted as an anatomical location for eligibility criteria. Each arm, each leg, and trunk are considered different anatomical locations.
4. Subject has severe pruritus, defined as WI-NRS  $\geq 7$  at the Screening Visit and a mean weekly WI-NRS  $\geq 7$  for the week (7 consecutive days) immediately prior to randomization (at least 5 days of recordings) on eDiary.
5. PN-IGA score of  $\geq 3$  (on a scale of 0-4, in which 3 is moderate and 4 is severe) at Screening and Baseline Visits
6. Sexually active female subjects must be:
  - postmenopausal, defined as at least 12 consecutive months post cessation of menses (without an alternative medical cause) and confirmed by a follicular stimulating hormone (FSH) test, or
  - surgically sterile following documented hysterectomy, bilateral salpingectomy, bilateral oophorectomy or
  - nonpregnant, nonlactating, and having agreed to use a highly effective method of contraception from the Screening Visit until 16 weeks after final study drug administration.
    - Note: highly effective methods of contraception include:

- hormonal contraceptives associated with inhibition of ovulation (stable dose for at least 4 weeks prior to first dose)
- intrauterine device
- intrauterine system
- double barrier methods of contraception (barrier methods include male condom, female condom, cervical cap, diaphragm, contraceptive sponge) in conjunction with spermicide.
- tubal ligation
- vasectomized male partner

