### **4.7 Selection of Study Population**

#### **4.7.1 Inclusion Criteria**

1. Male or female aged 18 to 80 years, inclusive, at the time of consent.
2. Have a physician-documented diagnosis of PN that is confirmed by review of medical photography (as outlined in the Study Manual) during the Screening Period. Duration of PN (since the time of first PN nodule) must be at least 6 months from the time of first PN nodule to Day 1, as affirmed by the subject.
3. Have at least 20 nodules of approximately 0.5 to 2 cm at the Screening Visit and Day 1. The nodules must be pruritic and present on at least 2 different anatomical locations (not be localized), involve the extremities, with extensor extremity involvement greater than the flexor extremity involvement. Nodules on the head (face and scalp) are not counted as an anatomical location for eligibility criteria. Each arm, each leg, and trunk are considered different anatomical locations.
4. Subject has severe pruritus, defined as WI-NRS  $\geq 7$  at the Screening Visit and a mean weekly WI-NRS  $\geq 7$  for the week (7 consecutive days) immediately prior to randomization (at least 5 days of recordings) on eDiary.
5. PN-IGA score of  $\geq 3$  (on a scale of 0-4, in which 3 is moderate and 4 is severe) at Screening and Baseline Visits.
6. Sexually active female subjects must be:
  - postmenopausal, defined as at least 12 consecutive months post cessation of menses (without an alternative medical cause) and confirmed by a follicular stimulating hormone (FSH) test, or

- surgically sterile following documented hysterectomy, bilateral salpingectomy, bilateral oophorectomy or
- nonpregnant, nonlactating, and having agreed to use a highly effective method of contraception from the Screening Visit until 16 weeks after final study drug administration.
  - Note: highly effective methods of contraception include:
    - hormonal contraceptives associated with inhibition of ovulation (stable dose for at least 4 weeks prior to first dose)
    - intrauterine device
    - intrauterine system
    - double barrier methods of contraception (barrier methods include male condom, female condom, cervical cap, diaphragm, contraceptive sponge) in conjunction with spermicide.
    - tubal ligation
    - vasectomized male partner

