7. Sexually active male subjects must have documented vasectomy or must agree to use a highly effective method of contraception as defined above with their partners of childbearing potential from first dose until 16 weeks after final study drug administration.
8. Male subjects must agree to refrain from donating sperm from first dose until 16 weeks after the last study drug administration. Female subjects must agree to refrain from donating eggs from first dose until 16 weeks after the last study drug administration.
9. Female of childbearing potential must have a negative serum  $\beta$ -human chorionic gonadotropin ( $\beta$ -hCG) test at the Screening Visit and negative urine pregnancy test on Day 1.
10. Able to comprehend and willing to sign an Informed Consent Form and able to abide by the study restrictions and comply with all study procedures for the duration of the study.
11. Subjects must be on optimized and stable treatment for co-morbidities for at least 28 days prior to Day 1.

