### **6.5                   Contraception**

Nonpregnant, nonlactating sexually active women of childbearing potential must agree to use a highly effective method of contraception from the Screening Visit until 16 weeks after final study drug administration.

- Note: highly effective methods of contraception include:
  - hormonal contraceptives associated with inhibition of ovulation (stable dose for at least 4 weeks prior to first dose)
  - intrauterine device
  - intrauterine system
  - double barrier methods of contraception (barrier methods include male condom, female condom, cervical cap, diaphragm, contraceptive sponge) in conjunction with spermicide.
  - tubal ligation
  - vasectomized male partner

Sexually active male subjects must have documented vasectomy or must agree to use a highly effective method of contraception as defined above with their partners of childbearing potential from first dose until 16 weeks after final study drug administration.

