#### 7.5.2              Pregnancy

Formal reproduction toxicology testing of KPL-716 has not yet been performed.

Female subjects of childbearing potential must therefore agree to use a highly effective and protocol approved contraceptive method ([Section 6.5](#)) for the duration of the study and until

16 weeks after last study drug administration under this protocol. Regular pregnancy tests will be performed for female subjects of childbearing potential, as defined in [Appendix 1](#).

Male subjects who have a female partner of childbearing potential must agree to use a highly effective and protocol approved contraceptive method ([Section 6.5](#)) for the duration of the study and until 16 weeks after last study drug administration under this protocol.

If a subject becomes pregnant while participating in the study, study drug dosing must be discontinued immediately.

A female subject must immediately inform the Investigator if she becomes pregnant during the study. A male subject must inform the Investigator if his female partner becomes pregnant during the study. Pregnancies occurring up to 16 weeks after last study drug administration must be reported to the Investigator. The Investigator must report all pregnancies to the Sponsor or designee immediately and no later than 24 hours of their first knowledge of the pregnancy. The Investigator should counsel the subject that it is unknown what effects study drug might have on a fetus. Monitoring of the subject should continue until conclusion of the pregnancy.

Instances of fetal death or congenital abnormality, if brought to the attention of the Investigator at any time after cessation of the study treatment and considered by the Investigator to be possibly related to the study treatment, must be reported to the Sponsor as an SAE.

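### No entry criterion bars a breastfeeding woman who is not sexually active, or who is surgically sterile under the second option of Inclusion 6

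*Protocol*

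**What the plan says.** Inclusion 6 reads the same in the synopsis and in Section 4.7.1. It begins "Sexually active female subjects must be" and gives three alternatives joined by *or*:

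- postmenopausal, confirmed by an FSH test;
- "surgically sterile following documented hysterectomy, bilateral salpingectomy, bilateral oophorectomy or";
- "nonpregnant, nonlactating, and having agreed to use a highly effective method of contraception", with a list of accepted methods that includes "tubal ligation".

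Outside the entry criteria, the word nonlactating appears only in Section 6.5: "Nonpregnant, nonlactating sexually active women of childbearing potential must agree to use a highly effective method of contraception".

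Two neighbouring criteria are not limited by sexual activity. Inclusion 9 requires pregnancy tests ("Female of childbearing potential must have a negative serum" β-hCG result at Screening, then a negative urine test on Day 1). Inclusion 8 states: "Female subjects must agree to refrain from donating eggs from first dose until 16 weeks after the last study drug administration".

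Section 7.5.2 records the state of the reproductive data: "Formal reproduction toxicology testing of KPL-716 has not yet been performed".

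**The concern.** The sponsor has already decided that a breastfeeding woman should not enter through the third option. Whether a woman is nursing does not depend on whether she is sexually active or has had pelvic surgery, and the protocol gives no reason to treat those women differently. The arrangement looks like a side effect of placing the lactation condition inside a contraception rule.

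What is at stake is possible exposure of a nursed infant to an investigational antibody. The infant is not a trial subject, and adverse event collection under Section 7.5.1.1 is directed at subjects. The matter is one of safety wording in the eligibility criteria; it does not bear on the statistical design.

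**Working it through.** No arithmetic applies. The check is to follow each kind of breastfeeding woman through the criteria, assuming that she meets all the disease, laboratory and medication requirements, and then to look for any other bar.

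**Through Inclusion 6**

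1. *Not sexually active.* The opening words of the criterion do not reach her, so none of its three options has to be met. She passes.
2. *Sexually active, with documented hysterectomy, bilateral salpingectomy or bilateral oophorectomy.* The second option is satisfied. Because the options are alternatives, the nonlactating condition in the third need not be met. She passes.
3. *Sexually active, with a tubal ligation.* Tubal ligation is not among the operations in the second option. It is a contraceptive method under the third, where nonlactating applies. She is barred.
4. *Sexually active, using any other listed contraceptive method.* She enters under the third option. She is barred.
5. *Postmenopausal.* The first option has no lactation condition either. However, 12 months without menses, no other medical cause and FSH confirmation make breastfeeding unlikely, so this route is not relied on.

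**Through everything else**

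- *Inclusion 8* binds all female subjects but concerns egg donation.
- *Inclusion 9* covers women of childbearing potential whether or not they are sexually active, but it tests for pregnancy only. A nursing woman who is not pregnant passes.
- *Exclusion 23* requires a medical or psychiatric condition and the opinion of the investigator or sponsor. It does not name lactation.
- *The other 27 of the 28 exclusion criteria* do not mention lactation or breastfeeding.
- *Section 6.5* describes which women owe a contraception commitment and is again limited to sexually active women.
- *Section 7.5.2* covers contraception, pregnancy testing and pregnancy reporting.
- *The Schedule of Activities (Appendix 1) and the SAP* contain no lactation restriction.

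**Pregnancy compared with lactation.** Both conditions appear in Inclusion 6 only in the third option. For pregnancy, Inclusion 9 closes the resulting gap for women of childbearing potential. For lactation no criterion does so. Routes 1 and 2 therefore stay open.

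**The case against.** **Section 7.5.2 may reach further than Inclusion 6.** It asks female subjects of childbearing potential to use approved contraception, without limiting this to the sexually active, and refers to Section 6.5, which describes the women it covers as nonlactating. This is fair evidence of intent. But the duty imposed is contraception, and no one is refused entry for breastfeeding. A surgically sterile woman is not of childbearing potential, so neither section reaches her.

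**Exclusion 23 is broader than risk to the subject.** It also covers interference with participation or assessments, compliance, and interpretation of results. An investigator could use it to turn away a nursing woman. It remains a case-by-case judgement about a medical or psychiatric condition, and it cannot be expected to work uniformly across about 75 planned centers.

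**Other documents may close the gap.** Section 5.2 binds investigators to the Investigator's Brochure and other study materials, and SAP Section 1 cites European and UK protocol versions. Neither these nor the consent form were available. This objection stands as a limit on scope: the finding concerns this protocol version only, and sites may have had the restriction from elsewhere.

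**The number affected is tiny.** This is accepted. The second route in particular requires current breastfeeding together with one of three operations, in a trial of about 180 subjects.

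A reader might go further and infer that breastfeeding women were dosed, or that the absent reproduction toxicology shows a risk to infants. The documents support neither. Section 7.5.2 mentions the missing testing to justify contraception, and nothing is said about transfer into milk. Adding up a mother's doses would not size the risk either: maternal dose is not infant exposure, and the full total would be relevant only if she nursed through the last open-label dose at Week 48.

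**Conclusion.** The point holds as a gap in the written criteria. Two groups of breastfeeding women can satisfy every listed entry criterion of this protocol version: those not sexually active, and those surgically sterile under the second option of Inclusion 6. Sexually active women relying on tubal ligation or another listed contraceptive method are not in the gap.

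The number affected cannot be counted from the documents; it is likely very small and may be zero. The size of any harm to an infant is unknown. The conclusion rests on reading Inclusion 6 literally, with its opening restriction and its alternatives joined by *or*, and on no unseen document supplying the bar.

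**What to change.** Add one stand-alone exclusion criterion to the synopsis and Section 4.7.2, for example: *Is breastfeeding at the Screening Visit or on Day 1, or does not agree to abstain from breastfeeding between the first dose and 16 weeks beyond the final dose; applies irrespective of sexual activity or surgical sterility.*

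The commitment over time matters, because a check at Screening and Day 1 alone would not stop a woman from resuming breastfeeding during dosing. The proposed period is the same as for egg donation in Inclusion 8, and it ends at the same point as the contraception rule. Inclusion 6 and Sections 6.5 and 7.5.2 can stay as they are.

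The cost is a wording amendment, which under Section 11.5 needs IRB/IEC approval, and regulatory approval where locally required, before use. The consent form and the European and UK versions need a matching check. Sites gain one eligibility question and no new test, and a very few women may be excluded. North American sites were already active when Version 6 was written (Appendix 13), so the change would protect only women screened after it takes effect. Bundling it with the next amendment keeps the burden low.

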**Multiple comparison/Multiplicity:**

As this is a dose finding study, there is no multiplicity adjustment planned for the comparisons of multiple doses of KPL-716 versus placebo.

**Determination of Sample Size:**

The Phase 2b sample size calculation is based on the primary efficacy endpoint (percentage change from baseline of WI-NRS at Week 16) using a two-sample t-test.

Approximately 180 subjects in total will be equally randomized to the 4 arms of Phase 2b. At Week 16, 53% and 30% reduction in weekly average of WI-NRS are assumed for KPL-716 and placebo arms, respectively. For each comparison, assuming treatment effect of 23% difference in weekly average WI-NRS reduction from baseline at Week 16 and standard deviation of 35%, and two-sided alpha of 0.05, 38 subjects in each arm will guarantee 80% power to the treatment effect. Approximately 45 patients in each arm are required after adjusting for 15% lost follow up.

**Randomization Strata:**

- Sex: Male vs Female
- Years since first nodule observation:  $\geq 10$  years vs  $< 10$  years

**Analysis Sets:**

**Modified Intent-to-Treat Analysis Sets:**

All randomized subjects who receive at least 1 dose of KPL-716 or placebo and have at least 1 post-baseline efficacy assessment in the double-blind Treatment Period will be included in the modified intent-to-treat (mITT) analysis set.

**Safety Analysis Sets:**

All randomized subjects who take at least 1 dose of KPL-716 or placebo will be included in the Safety Analysis Set.

**Per Protocol (PP) Analysis Sets:**

All mITT subjects who have no important protocol deviations that may potentially bias efficacy analyses of the study will be included in the PP set.

**Pharmacokinetic (PK) Analysis Sets:**

Subjects who received KPL-716 and who had at least one PK sample will be included in the PK population.

**Analysis of Efficacy:**

The primary efficacy endpoint in Phase 2b will be analyzed with ANCOVA including treatment as fixed effect, baseline WI-NRS, and randomization as covariates. Details will be specified in the Phase 2b SAP.

**Analysis of Safety:**

All safety analyses will be conducted based on the Safety Analysis Set. Summary tables will be done for safety endpoints (treatment emergent AEs, labs, vital signs, etc.). All safety data will be listed by subject. Details for the analysis of safety data will be provided in the SAP.

**PK Analyses:**

For all subjects, serum samples will be collected before each dose at time points shown in [Appendix 1](#) in order to quantify concentrations of KPL-716. Descriptive statistics will be calculated for the serum concentrations of KPL-716 by visit. Individual listings of plasma concentrations will be provided.

**Biomarker Analyses:**

Skin and blood biomarker levels will be analyzed.

[figure not shown]
**Immunogenicity Analyses:**

Serum ADA will be listed and summarized by treatment group and overall using descriptive statistics.

**Interim Analysis:**

An interim analysis for Phase 2b portion may be conducted after at least 50% subjects complete Week 16 Visit. If the interim analysis is conducted in the Phase 2b part, a two-sided alpha of 0.0001 will be spent. The two-sided alpha level for the final Phase 2b efficacy analysis will be 0.05. Additional details regarding the interim analysis, if performed, will be provided in the SAP along with other analysis plans.

Figure 1 Phase 2b Study Design Diagram

## LIST OF ABBREVIATIONS

Abbreviation or Specialist Term	Explanation
ADA	anti-drug antibodies (anti-KPL-716 antibodies)
AE	adverse event
AESI	AE of special interest
Anti-HBc	hepatitis B core antibody
Anti-HBs	hepatitis B surface antibody
ASR	Accurate Symptom Reporting
ATC	Anatomical Therapeutic Chemical
AUC 0-∞	Area under the concentration-time curve from time zero to infinity
β-hCG	β-human chorionic gonadotropin
BMI	body mass index
C max	maximum concentration
CRO	Clinical Research Organization
EDC	electronic data capture
ECG	electrocardiogram
eCRF	electronic Case Report Form
EOS	end of study
FSH	Follicle-stimulating hormone
GAD-7	General Anxiety Disorder
HBV	hepatitis B virus
HbsAg	hepatitis B surface antigen
HCV	hepatitis C virus
HIV	human immunodeficiency virus
IB	Investigator's Brochure
ICF	Informed Consent Form
ICH	International Council for/Conference on Harmonization
IEC	International Ethics Committee
IGA-CNPG-A	Investigator's Global Assessment for Prurigo Nodularis-Activity
IGA-CNPG-S	Investigator's Global Assessment for Prurigo Nodularis-Stage
IMP	investigational medicinal product
IRB	Institutional Review Board
ISR	injection site reaction
IWRS	interactive web response system
LIFR	leukemia inhibitory factor receptor
MedDRA	Medical Dictionary for Regulatory Activities
NOAEL	no observed adverse effect level
NRS	Numerical Rating Scale
OSM	oncostatin M
OSMRβ	oncostatin M Receptor beta
PD	pharmacodynamic(s)
PGI-PN-S	Patient Global Impression of Prurigo Nodularis Severity
PGIC	Patient Global Impression of Change
PHQ-9	Patient Health Questionnaire

Abbreviation or Specialist Term	Explanation
PK	pharmacokinetic(s)
PN	prurigo nodularis
PN-IGA	Prurigo Nodularis Investigator Global Assessment
PP	per-protocol
PRR	Placebo Response Reduction
PT	preferred term
Q	quartile
QTcF	QT interval corrected for heart rate using Fridericia's method
SAE	serious adverse event
SAP	Statistical Analysis Plan
SC	subcutaneous(ly)
SOC	System Organ Class
SRT	Safety Review Team
TEAE	treatment-emergent adverse event
ULN	upper limit of normal
VAS	Visual Analog Scale
WI-NRS	Worst Itch Numeric Rating Scale

## 1 INTRODUCTION

### 1.1 Background

Prurigo nodularis (PN) is a chronic skin disease characterized by symmetrically distributed, intensely pruritic hyperkeratotic nodules most frequently affecting extensor extremities and the trunk (1, 2). PN is recognized as the nodular subtype of a recently described umbrella condition called Chronic Prurigo, which encompasses a larger variety of lesions ranging from papule to umblicated ulcers to plaques (1).

There are no approved therapies for PN. Topical therapies such as topical corticosteroids, calcineurin inhibitors, calcipotriol, and capsaicin, systemic corticosteroids, thalidomide, systemic immunomodulatory drugs such as methotrexate and cyclosporin, antiepileptics and antidepressants, phototherapy and photochemotherapy are often tried with limited success and in some cases with unfavorable risk benefit ratio (3). As a result, PN carries a significant unmet medical need as the intractable itching, the intense scratching and the ensuing skin lesions lead to sleep loss, embarrassment, anxiety, and depression and overall diminish quality of life (4).

Histologically, PN is characterized by thick compact orthohyperkeratosis, irregular epidermal hyperplasia, increased capillaries, an inflammatory infiltrate consisting of mainly lymphocytes and macrophages and to a lesser degree eosinophils and neutrophils, increased fibroblasts, and vertical fibrosis of the papillary dermis (5). Although the exact etiology of PN is unknown, the symptomatology of the disease implicates pruritic pathways and its histologic features point to epidermal activation, inflammation, and fibrosis.

PN is associated with a number of co-morbidities including infections (HIV and hepatitis C), chronic kidney disease, malignancies, endocrine, hematologic, gastrointestinal, cardiovascular, pulmonary, dermatologic and psychiatric conditions (6, 7). Chronic pruritus is a feature of many of these co-morbidities. In a subset of patients with chronic pruritus, whether idiopathic in origin or in association with a co-morbidity, chronic pruritus and chronic scratching lead to neuronal sensitization and the onset of a vicious itch-scratch cycle that ultimately results in the development of nodules. Although chronic pruritus in the context of an underlying condition can trigger PN, once PN develops its clinical course and severity appear to be independent of the original underlying condition such that treatment of the underlying condition is not sufficient to treat PN (1).

In addition to published studies describing cohorts of PN patients (6, 7, 8, 9), Kiniksa undertook an observational study, which enrolled 54 PN patients in the United States and Europe, to understand better the clinical manifestations, standard of care management, natural history and pathogenesis of the disease (Data on file at Kiniksa). In approximately 13% to 50% of patients, no underlying condition was identified as the trigger for the chronic pruritus that led to PN suggesting that some patients may have an idiopathic form of the disease (7 and Data on file at Kiniksa). The two largest published studies, with 108 patients in Germany and 909 patients in the US, found atopic dermatitis in association with PN in only 7 and 10.7% of PN patients, respectively (6, 7). Although atopic dermatitis is not a common underlying condition in PN, atopic disposition is believed to be prevalent with 46% and 65% of patients described to have atopic diathesis in 2 separate studies (7 and 9). Whether presence of atopy impacts the pathogenesis of PN and/or its clinical course and whether it defines a specific subset of patients remains to be seen. In a broader sense, it also remains to

be seen whether the presence or absence of an underlying condition or the type of underlying condition impacts the mechanism of disease in PN or whether all circumstances lead to a common pathway of chronic pruritis that drives disease pathogenesis in PN.

The primary objective of this study is to investigate the efficacy of KPL-716 in reducing pruritus in PN. The secondary objectives are to investigate the impact of KPL-716 on sleep loss, quality of life and disease severity. Clinical response and/or biomarker studies will be used to understand whether KPL-716 responsiveness is limited to a specific subset of patients with PN. For the rationale of the study, please see [Section 1.3](#).

